Research design: We will conduct a up to twelve-month longitudinal surveillance study of miners at the intervention site (n=less than 250) in McKinley County, NM, and control site (n=less than 350) in Campbell County, WY. Both surface coal mines, operated by the same company, have similar engineering, administrative, and personal protective measures in place, including SARS-CoV-2 symptom & fever screening. While there will be frequent point-of-care molecular testing at the intervention site, seropositivity (baseline, 3, 6, and approximately12 m) will be measured at both sites.

3.4. Specific Aim 4:

Factors impacting SARS-CoV-2 spread is not well studied in rural essential workers outside healthcare. Our *objective* is to examine novel factors affecting the spread of infection in miners. A recent epidemiological study reported high COVID-19 mortality in communities exposed to ambient particulate air pollution (11). This novel risk factor is relevant for miners who are exposed to high levels of particulate air pollution at the workplace. Further, although the CDC encourages the public use of a cloth face-covering, its use by miners may vary, based upon individual and community factors (38), and has not been adequately studied. Our working *hypothesis 4A* is that miners with incident infection demonstrate less frequent use of cloth face-coverings outside the workplace, greater mine dust exposure intensity, presence of dust-related lung disease, and racial/ethnic minority status than those not infected. *Hypothesis 4B:* Test and vaccine uptake in miners is predicted by specific barriers and facilitators. The *rationale* for the proposed work is to prevent the spread of COVID-19 infection. We expect that our findings will result in novel primary prevention strategies for workers in dusty trades.

Research design: This is a up to twelve-month longitudinal surveillance study at the intervention (n=less than 250) and control (n=less than 350) mines.

4. Inclusion and Exclusion Criteria

All miners will be recruited at the mine site with the support of mine leadership.

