At the beginning of each alternate shift, the mine safety team will collect a supervised self-collected nasal swab from each worker for point-of-care screening testing, as described in Aim 1. Fingerstick or venipuncture blood samples will be obtained at the mine site from all study participants at the time of enrollment, and at 3, 6, and approximately 12 months (no more than 24 ml or 4.9 teaspoons each visit) to determine seropositivity, using the COVID-19 IgG/IgM antibody test. Employee absenteeism (both general and screen test results-driven) and coal production records will be analyzed.

12.4. Specific Aim 4:

Predictor variables are listed in Table titled Overview of Study Procedures. Database management and timeline will be similar to that for Aim 1.

13. Data Analysis

13.1. Specific Aim 1:

Predictor and Outcome variables: Test acceptance by miners is measured for each eligible work shift and cumulative acceptance rate (i.e., outcome) is calculated over the study timeframe (frequency of tests /number of eligible shifts worked, max number estimated at less than 120). Characteristics predicting acceptance include self-reported educational and racial/ethnic minority status (from baseline questionnaire), self-reported prior SARS-CoV-2 infection or vaccination (from app), evidence of prior infection (from a prior positive screening test), and daily county incidence and prevalence infection rates (from publicly available data).

Statistical approach: Cumulative acceptance rate will be compared between groups, defined by predictive characteristics. Poisson regression with indicator variables will be used to assess the effects of miner characteristics on cumulative acceptance rates. Analyses will use the number of shifts in which tests were available to miners for the rate denominator (offset) to account for absenteeism. Longitudinal analysis of shift-level acceptance by miners will be examined using mixed model regression for binary outcomes that account for repeated measures. Within-miner factors will include time-varying SARS-2-COV-2 exposure (personal and community) and vaccination status, and linear and nonlinear time trends.

PROTOCOL TITLE: Keeping rural minority ‘essential’ workplaces open safely during the COVID-19 pandemic: The role of frequent point-of-care molecular workplace surveillance for miners

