Predictor and Outcome variables: The predictor variable is the mine status. The primary outcome is any new seropositivity for SARS-CoV-2 IgM or IgG at 3, 6, or 12 months relative to baseline. The test allows for the qualitative detection of IgG and/or IgM antibodies (separately) against SARS-CoV-2, indicating recent (IgM: 3-5 days) or prior infection (currently unknown). The tests have positive percent agreements of 97% and 87% and negative percent agreements of 98% and 99% for IgG and IgM, respectively, compared to oropharyngeal swab RT-PCR. We will also study the presence of symptoms or fever, irrespective of infection status, as an alternative study outcome for hypothesis 3A. Costs of the test-based surveillance program, employee absenteeism patterns, and mine coal production will contribute towards defining the outcome variables for hypothesis 3B. At a minimum, a valuable outcome is to determine surveillance program costs, which have not been previously established for this rural industry setting, organization size, or proposed surveillance frequency. Additionally, variance in outcome measures—defined as employee days lost due to incident infection, mine productivity, and reduction in worksite infection rate—across the two sites will be used to estimate the cost-effectiveness of the intervention. Database management and timeline are similar to that for Aim 1.

PROTOCOL TITLE: Keeping rural minority ‘essential’ workplaces open safely during the COVID-19 pandemic: The role of frequent point-of-care molecular workplace surveillance for miners

Covariates: Baseline seropositivity, vaccination status, other host susceptibility and vulnerability factors outlined in Table 1, and daily community prevalence and incidence, will be studied as covariates in multivariable models (35).

Statistical analysis: Chi-square tests will examine whether relative frequencies of incident seropositive miners are the same at 3-months, 6-months, and 12-months for the two mine types, using $\alpha=0.025$ to account for the two tests. Generalized linear models for repeated binary outcomes will be used to assess how covariates are associated with seropositive status over time.

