Power calculation: Based on representative seroprevalence/molecular prevalence rates for similar communities (36), we anticipate a 10% baseline seropositivity with incident seropositivity at 6 months at 5% for the intervention mine and a baseline seropositivity of 5% in the control mine. We anticipate similar power calculations to apply up to 12 months. We explored a range of control miner incident seroprevalence values that would have 80% power when comparing frequencies at the two mines using chi-square tests. We expect 80% power if incident seropositivity at the control mine is $\geq 9\%$ ($\alpha=0.025$).

13.4. Specific Aim 4:

Statistical analysis: Chi-square and logistic regression analyses will be used to explore how miner characteristics are associated with baseline seropositivity. Generalized linear models for repeated binary outcomes will be used to assess how predictor variables (noted in Table 7) and covariates (as noted in Aim 3) are associated with incident seropositivity at 3, 6, & approximately 12 months. Both analysis strategies will include mine type as a covariate and will add predictor and outcome variables noted in Table 7.

Table 7: List of predictor and outcome variables for Aim 4

Predictor and outcome variables	Time of measurement	Procedure for ascertainment
Frequency of cloth face-covering use outside the mine	On the day of the screening test; Mean summary variable over the one week before the test	Self-report, via the app, every work shift
Occupational dust exposure intensity	On the day of the screening test; Mean summary variable over the one week before the test	Mine safety team, via job-exposure matrix, every shift
Presence of lung disease	Baseline	Baseline survey
Race/ethnicity status	Baseline (at study enrollment)	Self-report via questionnaire
Facilitators and barriers	Between 6 and 12 months	Self-report via questionnaire
Test and vaccine uptake	Between 6 and 12 months	Self-report via questionnaire

Power calculation: We assessed power, using simulation for incident seropositivity at 6 months with mine type as covariate and a predictor miner variable, such as high dust exposure. We anticipate similar power calculations up to 12 months. We assumed the miner variable, present in 1/3 sample, will increase the probability of incident seropositivity by 0.10. For a logistic regression analysis and this setup, power is $>96\%$.

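### Aim 3 compares the mines at three visits but sets alpha for two tests, so the implied 5% overall error level is not guaranteed

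*Combined protocol and SAP*

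**What the plan says.** Under Statistical analysis in Section 13.3, chi-square tests are to examine whether "relative frequencies of incident seropositive miners are the same at 3-months, 6-months, and 12-months for the two mine types". The same sentence sets alpha at 0.025 "to account for the two tests".

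The primary outcome in that section is "any new seropositivity for SARS-CoV-2 IgM or IgG at 3, 6, or 12 months relative to baseline". Three post-baseline blood draws are confirmed in Section 3.3 ("seropositivity (baseline, 3, 6, and approximately12 m) will be measured at both sites"), in Section 12.3 (samples "at the time of enrollment, and at 3, 6, and approximately 12 months") and in the overview table of Section 12.

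The power calculation in Section 13.3 is made at 6 months with the same alpha of 0.025: 5% incident seropositivity in the intervention mine, and 80% power claimed if the control mine reaches 9% or more. It then adds: "We anticipate similar power calculations to apply up to 12 months".

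The plan names no primary visit, testing order or gatekeeping rule, does not say which two tests are meant, and states no overall error level.

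**The concern.** The plan chose to adjust for multiplicity, and its adjustment does not match its own list of tests. An alpha of 0.025 is a Bonferroni split of 5% over two tests; three visits are tested. The stated threshold therefore does not secure the level it appears to be built for.

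This bears on hypothesis 3A, the effectiveness claim. Two related matters are also left open and could be settled after the data are seen:

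- what is concluded if only one of the three visits is significant;
- whether a miner counted at 6 or 12 months is one who has become positive at any time since baseline, or only since the previous draw.

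**Working it through.** **Inputs from the plan.** Per-test alpha 0.025 and three test times (13.3, Statistical analysis); rates of 5% and 9% (13.3, Power calculation); fewer than 250 intervention and fewer than 350 control miners (3.3 and 5).

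**Assumptions.** Group sizes of 250 and 350, the upper limits. Overall level 5%. Two-sided Pearson chi-square without continuity correction. For the null simulations, equal 12-month cumulative incidence in both mines of 10%, 15%, 18% or 20%.

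**Step 1: reproduce the plan's alpha.** 0.05/2 = 0.025, an exact match to two tests. Three tests would give 0.05/3 = 0.0167.

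**Step 2: what three tests at 0.025 guarantee.**

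- Bonferroni bound: 3 x 0.025 = 0.075.
- If the tests were independent: 1 - (1 - 0.025)^3 = 0.0731.

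**Step 3: allow for correlation between visits.** With cumulative outcomes and constant incidence, the test statistics correlate at about sqrt(3/6) = 0.71, sqrt(6/12) = 0.71 and sqrt(3/12) = 0.50. A trivariate normal calculation then gives 0.059. With equal pairwise correlation the error is 0.0515 at 0.80 and 0.0482 at 0.85, so it falls below 5% only when the correlation lies above about 0.8.

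**Step 4: simulate under the null**, 400,000 replicates per scenario. The Monte Carlo standard error near 6% is sqrt(0.06 x 0.94/400,000) = 0.0004.

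| Tests and outcome | Share of cases in months 0-3 / 3-6 / 6-12 | Family-wise error |
|---|---|---|
| Three at 0.025, cumulative | 70 / 15 / 15% | 4.5% |
| Three at 0.025, cumulative | 50 / 25 / 25% | 5.2-5.3% |
| Three at 0.025, cumulative | 25 / 25 / 50% (constant incidence) | 5.9-6.1% |
| Three at 0.025, cumulative | 10 / 20 / 70% | 5.8-6.4% |
| Three at 0.025, new since last draw | all splits | 6.3-7.3% |
| Two at 0.025, cumulative (3 and 6, or 6 and 12 months) | all splits | 3.5-4.7% |
| Three at 0.0167, cumulative | all splits | 3.0-4.2% |
| Three at 0.0167, new since last draw | all splits | 3.7-4.8% |

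The new-since-last-draw analysis uses miners still negative as the denominator. Removing the anticipated baseline positives (250 x 0.90 = 225; 350 x 0.95 = 332.5, taken as 332) moves the first three rows only to 4.5-6.2%.

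**Step 5: try other readings of the two tests.**

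- IgG and IgM: the outcome pools them, and testing each at three visits would make six comparisons.
- The two mine types: they give one comparison per visit.
- A single ever-positive outcome over the year: that is one test.

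None gives two.

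**Step 6: power at 5% versus 9%**, since the power statement carries the same alpha. Power = Phi[(0.04 - z x se0)/se1], where the pooled rate is (12.5 + 31.5)/600 = 0.0733, se0 = sqrt(0.0733 x 0.9267 x (1/250 + 1/350)) = 0.0216 and se1 = sqrt(0.05 x 0.95/250 + 0.09 x 0.91/350) = 0.0206.

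- At 0.025 (z = 2.241): 34%.
- At 0.0167 (z = 2.394): 28.5%.
- At 0.05 (z = 1.960): 46%.

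The claimed 80% is not reached at any of these levels. That shortfall is a separate error, and the choice of alpha explains little of it.

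**The case against.** The strongest reply is that the effect is small on the reading the text best supports. The outcome is defined relative to baseline, which points to a cumulative count. On that reading the error runs from 4.5% to 6.4%: under 5% when cases come early and at most 1.4 points above it otherwise. This stands, and it is why the claim is that 5% is not guaranteed, not that it is always exceeded.

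The 5% level is inferred and never written. That also stands, though no other round overall level explains 0.025 over two tests.

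Splitting alpha conventionally means that any one significant test counts as success, so a decision rule may be implied. Partly granted: the convention exists, but the plan does not state it, and the count behind it is wrong.

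The origin may be innocent. The power calculation is at 6 months with 12 months added, and the cap on eligible shifts is under 60 in Section 7.1 but under 120 in Section 13.1. An alpha set for 3 and 6 months, before a 12-month visit was added, would explain the wording. This is conjecture, and it would not repair the current text, but it does suggest a simple fix: name two confirmatory visits.

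Finally, the study is described as proof of principle, the mines are not randomised, and covariate-adjusted repeated-measures models are also planned. Site differences may well matter more than a point or so of type I error. That is fair. The figures here concern multiplicity alone under equal incidence and say nothing about confounding.

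**Conclusion.** The concern holds. Section 13.3 lists three tests and adjusts for two, and nothing elsewhere in the document reconciles the count. The guaranteed bound is 7.5% against an implied 5%. The realised error is about 4.5-6.4% for a cumulative outcome and 6.3-7.3% for an outcome counted by interval, given 250 versus 350 miners, equal incidence at the mines, and 12-month incidence of 10-20%. It should be fixed because it sets the threshold for the effectiveness hypothesis and leaves the decision rule open, even though the numerical excess is modest.

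**What to change.** State the overall error level in Section 13.3, and adopt one of these:

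- **(a)** one primary visit tested at 0.05, the others secondary;
- **(b)** a fixed order of the three visits, each at 0.05, stopping at the first non-significant result;
- **(c)** all three confirmatory, at 0.05/3 = 0.0167 each or with Holm across the three p-values;
- **(d)** two named confirmatory visits at 0.025, the third supportive.

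State also whether incident seropositivity at each visit is cumulative since baseline or new since the last draw. Then recompute the power statement at the resulting alpha (for Holm, conservatively at 0.0167).

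The cost is a few sentences of text, with no change to conduct or data collection. Relative to the present 0.025, options (a) and (b) raise power at the first-tested visit (46% against 34% at 5% versus 9%), (c) lowers it to 28.5%, and (d) leaves it unchanged. Recomputing will expose the separate shortfall from 80% under every option.

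Timing matters. Section 6 starts analysis in July 2021 while data collection runs to March 2022. The visits, the order and the definition of incident should be fixed and dated before between-mine results are seen. If some have already been seen, say so; option (c) is then safest, because it requires no choice among visits.

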4.2. Exclusion Criteria

- Unable or unwilling to provide and sign Informed Consent Form
- < 18 years of age.

PROTOCOL TITLE: Keeping rural minority ‘essential’ workplaces open safely during the COVID-19 pandemic: The role of frequent point-of-care molecular workplace surveillance for miners

We will not recruit or enroll pregnant women, incarcerated individuals, minors, or adults unable to consent.

5. Number of Subjects

Less than 600 subjects will be recruited at all mine sites in this longitudinal study. Of these, less than 250 miners will be recruited from the Peabody El Segundo mine in McKinley County, NM at the edge of Navajo Nation (i.e., intervention mine). The remaining less than 350 miners will be recruited from the Peabody Caballo and Rawhide mines at Campbell County, WY (i.e., control mine). Both surface coal mines, operated by the same company, have similar engineering, administrative and personal protective measures in place, including SARS-CoV-2 symptom & fever screening. While there will be frequent point-of-care molecular testing at the intervention site, seroprevalence (baseline, 3, 6, and 12 m) will be measured as an outcome at both sites.

6. Study Timelines

The duration of individual subject’s participation in this research is estimated to be approximately 12 months from the time they give and sign informed consent. We anticipate that all study participants will be enrolled in the first month of the recruitment and enrollment. Below are milestones with estimated dates of completion. The dates may be adjusted as necessary depending on the completion of previous milestones.

Milestone 1: Completion of planning, contracts, purchase of tests and supplies, protocols and IRB approval: by January 2021.

Milestone 2: Recruitment and collection of data: January 2021 through March 2022 (anticipated).

Milestone 3: Data analysis and dissemination: July 2021 through November 2022 (anticipated).

7. Study Endpoints:

7.1. Specific Aim 1:

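### Aim 3's stated 80% power (5% vs 9% incident seropositivity, alpha 0.025) is not attainable: the planned chi-square test has about 34% at the enrolment ceiling

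*Combined protocol and SAP*

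**What the plan says.** The power paragraph of section 13.3 (Specific Aim 3) fixes "incident seropositivity at 6 months at 5% for the intervention mine". It then looks for the control-mine rate that gives 80% power when "comparing frequencies at the two mines using chi-square tests", and concludes: "We expect 80% power if incident seropositivity at the control mine is" 9% or higher, at alpha 0.025. It adds that similar calculations should hold up to 12 months.

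The alpha comes from the statistical analysis paragraph of the same section, "using $\alpha=0.025$ to account for the two tests". The power paragraph gives no sample size, sidedness or allowance for dropout. The sizes are in section 3.3, which describes surveillance "at the intervention site (n=less than 250) in McKinley County, NM, and control site (n=less than 350) in Campbell County, WY". Section 5 repeats them: "less than 250 miners will be recruited from the Peabody El Segundo mine" and "The remaining less than 350 miners will be recruited from the Peabody Caballo and Rawhide mines".

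The power paragraph also anticipates baseline seropositivity of 10% at the intervention mine and 5% at the control mine. Sections 7.3 and 13.3 define the primary outcome as seropositivity that is new relative to baseline.

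**The concern.** A 4-point difference between two low proportions, tested at 0.025 with at most 600 people, cannot plausibly carry 80% power. At the ceiling the expected counts are only 250 × 0.05 = 12.5 and 350 × 0.09 = 31.5 incident cases.

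The figure matters because hypothesis 3A is the study's effectiveness claim and this is Aim 3's primary outcome. A reader who trusts the stated 80% would take a non-significant result as fair evidence against a 4-point effect. If the real power is near one third, such a result says little, and a useful preventive measure could be dismissed on it.

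**Working it through.** **Inputs, all from the document**

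- Intervention rate p1 = 0.05 and control rate p2 = 0.09 (13.3, power calculation).
- Alpha = 0.025 per test (13.3). A chi-square test on two proportions is two-sided by construction, so z = 2.2414.
- n1 = 250 and n2 = 350 (3.3 and 5). Both are ceilings.
- Baseline seropositivity 10% and 5% (13.3), so at most 250 × 0.90 = 225 and 350 × 0.95 = 332.5 (332 used) are seronegative at the start.

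**Formula (two-sample chi-square, pooled variance under the null)**

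- p̄ = (n1·p1 + n2·p2)/(n1 + n2)
- SE0 = √[p̄(1 − p̄)(1/n1 + 1/n2)]
- SE1 = √[p1(1 − p1)/n1 + p2(1 − p2)/n2]
- Power = Φ[(|p2 − p1| − z·SE0)/SE1]

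**Attempt to reproduce the plan's 80%, at 250/350**

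- p̄ = (12.5 + 31.5)/600 = 0.0733
- SE0 = 0.02159 and SE1 = 0.02059
- (0.04 − 2.2414 × 0.02159)/0.02059 = −0.407, and Φ(−0.407) = **34.2%**

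Exact enumeration of the Pearson chi-square test gives 33.9%, or 28.7% with a continuity correction. The 80% is not reproduced.

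**At 225/332 (baseline-seronegative miners only)**

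- p̄ = 0.0738, SE0 = 0.02258, SE1 = 0.02140
- (0.04 − 2.2414 × 0.02258)/0.02140 = −0.496, so power = **31.0%** (exact 31.5%)

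**Other readings at 5% vs 9%**

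| Reading | Power |
|---|---|
| 250/350, two-sided 0.025, arcsine formula | 37.1% |
| 250/350, two-sided 0.025, unpooled formula | 38.3% |
| 300/300, two-sided 0.025 | 37.4% |
| 250/350, two-sided 0.05 (same as one-sided 0.025) | 45.5% |
| 250/350, one-sided 0.05 | 58.6% |
| 250/350, one-sided 0.05, unpooled formula | 61.7% |

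Reading the 9% as an increment (5% vs 14%), which the wording does not support, gives 92.8%. That does not match 80% either.

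**What 80% power would require at two-sided 0.025**

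- Holding the intervention rate at 5% and solving the formula for p2 gives a control rate of 12.2% at 250/350 and 12.7% at 225/332.
- Holding 5% vs 9% and the 1:1.4 ratio gives 675 + 945 = 1,620 miners. Against the ceiling, 1,620/600 = 2.7.

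**The case against.** The power paragraph states no sample size, so strictly the claim is that 80% cannot be reproduced from the only sizes the document gives. That is true, but those sizes are upper limits. Smaller groups, dropout or a continuity correction would only lower the figure.

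Two non-planned routes land near 80%. One treats the intervention mine's 5% as a known constant and tests the control mine alone against it. With n = 332 this is Φ[(0.04 − 2.2414 × √(0.05 × 0.95/332))/√(0.09 × 0.91/332)] = 79.9%, and with n = 350 it is 81.8%. The other counts three visits per miner as independent observations (750/1,050), giving 84.5%, or 80.9% at 675/996. Either might explain where 80% came from, but the document describes neither. Section 13.3 compares two mines at each time point, and the intervention rate is itself estimated with error.

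Two qualifications stand. The 225/332 denominator is an inference. Baseline serostatus is also listed as a covariate, and IgM and IgG are read separately, so some baseline positives might stay in the analysis. In addition, 34% describes the 6-month rates. If both rates doubled by 12 months, to 10% and 18% (an assumption made here for illustration), power would be about 70% at 250/350 and 65% at 225/332, still short of 80%.

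**Conclusion.** The stated 80% is wrong for the planned test. For 5% vs 9% with a two-sided 0.025 Pearson chi-square, power is about 34% at the enrolment ceiling, and about 31% if only baseline-seronegative miners count. The type II error is therefore about 66–69%, not 20%. The smallest control rate with 80% power is about 12.2–12.7%, not 9%.

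The result rests on the document's own rates, alpha and enrolment caps. No choice of alpha, sidedness or standard two-sample formula that was tried exceeds about 62%. The calculation treats miners as independent; variation between mines would reduce power further and is not quantified here. Because this is the power of the primary effectiveness comparison, it must be corrected.

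**What to change.** Rewrite the power paragraph in section 13.3 to say the following:

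- With at most 250 and 350 miners (about 225 and 332 if baseline positives are excluded), a two-sided chi-square test at alpha 0.025 has about 31–34% power for 5% vs 9%.
- 80% power requires a control rate of about 12.5%.
- The sample sizes, sidedness, at-risk denominator and dropout allowance used are given explicitly.

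The sentence extending the calculation to 12 months should be recomputed with stated 12-month rates, or removed. Section 13.3 divides alpha for two tests but lists three time points. If that is settled as 0.05/3 = 0.0167, the control rate needed becomes about 13% (12.7% at 250/350, 13.1% at 225/332).

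Add a commitment to report the risk difference between mines with its confidence interval, and not to interpret non-significance as absence of effect.

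The cost is wording only. Enrolment and design do not change, but the stated power becomes much less favourable.
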